8.8.5. Median disease duration

Survival time will be analysed with the R package *survival*. Time zero for the survival analysis is the date of first diagnosis. Patients for whom no date of death is recorded will be censored at the date of end of their observation period or administratively censored at the end of study period.

Median survival time, i.e. disease duration, will be estimated with 95% CI using Brookmeyer-Crowley method [4].

8.8.6. Indirect estimated prevalence

From the overall incidence (I) and median disease duration (D) the indirect prevalence will be calculated with formula

$$P = I \cdot D \tag{1}$$

A CI for this indirect estimated prevalence will be generated by using the relation on the log scale:

$$\log P = \log(I \cdot D) = \log I + \log D \tag{2}$$

hence for the variance

$$Var(\log P) = Var(\log I) + Var(\log D) + 2 \cdot Cov(\log I, \log D)$$
(3)

This will be calculated using

$$Var(\log I) = 1/C \tag{4}$$

where C is the total number of cases used for the calculation of the incidence I.

An approximation of $Var(\log D)$ will be generated using the limits D_{low} and D_{upp} of the 95% CI for D:

$$Var(\log D) = \left(\left(\log D_{upp} - \log D_{low} \right) / (2 \cdot 1.96) \right)^2$$
(5)

We will assume incidence rate and disease duration are independent, hence

$$Cov(\log I \cdot \log D) = 0 \tag{6}$$

With the obtained variance of $Var(\log P)$ a 95% CI for $\log P$ will be calculated and then converted to a CI for *P*.

8.9 Evidence synthesis

Estimated direct prevalence, incidence and median survival will be reported separately for each database. In addition, the results will be combined across data sources. To this end, a random-effect meta-analyses model will be fitted for all the results described below:

- 1. The direct estimated point prevalence. This will be done using the function metaprop of the R *meta* package using as input the numerators and denominators utilised to calculate the point prevalence in each database.
- 2. The incidence rate. For this meta-analysis, function metarate of the *meta* R package will be used with input the total number of events and the total number of person years in each database.
- 3. The median disease duration. For this meta-analysis, the function metagen of the *meta* R package will be used. Depending on the skewness of the CIs of the medians *D*, meta-analysis will be performed on log*D*. Input will be the estimates and the approximated standard errors calculated as described above in 8.8.6. equation (5).
- 4. The indirect estimated prevalence. For this meta-analysis, function metagen of the *meta* R package will be used. Meta-analysis will be performed on log*P*. Input will be the estimates and the approximated standard errors calculated as described above in 8.8.6. equation (3).

Forest plots and measures of statistical heterogeneity between data sources will be reported in addition to the combined results of the quantities of interest listed above.

For each of the results in 1) to 4) above, it might be that not all databases provide an estimate, for example, because the number in a numerator might be below the minimum value of 5 or the median disease duration might not be observed in the available data. Meta-analysis will be done with estimates available.

Finally, we will also calculate an indirect prevalence using the combined results for incidence and median disease duration.

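### Section 8.9 item 3 allows median duration to be pooled on the natural scale but supplies only a log-scale standard error, so that branch gives wrong weights, interval and heterogeneity

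*Protocol*

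**What the plan says.** Protocol section 8.9 states that "a random-effect meta-analyses model will be fitted for all the results described below", and item 3 of the list that follows is the median disease duration, pooled with metagen. The scale is left conditional: "Depending on the skewness of the CIs of the medians" D, the analysis is to be done on log D. No degree of skewness is named, and the wording implies that D itself is pooled otherwise. The next sentence covers both cases: "Input will be the estimates and the approximated standard errors calculated as described above in 8.8.6. equation (5").

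Section 8.8.6 introduces equation (5) as an approximation of Var(log D) that "will be generated using the limits" of the 95% interval for D. It is the squared difference of the log limits divided by 2 × 1.96. Those limits come from section 8.8.5: "Median survival time, i.e. disease duration, will be estimated with 95% CI using Brookmeyer-Crowley method".

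Item 4, the indirect prevalence, is fixed on log P and uses equation (3), which is on the same scale. Section 8.9 ends with a further use of the pooled duration: "we will also calculate an indirect prevalence using the combined results for incidence and median disease duration".

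**The concern.** Inverse-variance pooling needs each estimate and its standard error on the same scale. The log D branch meets this once the square root of equation (5) is taken. The natural-scale branch does not: it pairs an estimate in years, months or days with an error that has no unit. The protocol gives no standard error for untransformed D anywhere.

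At stake are the pooled duration, its interval, the heterogeneity measures and forest plot promised for it, and the closing indirect prevalence built from pooled D. In a study meant to compare direct and indirect prevalence, spurious heterogeneity between databases, or an interval that is too narrow, would colour the discussion of whether the indirect method works.

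**Working it through.** The protocol gives no medians, intervals or pooled values, so there is no figure of its own to reproduce. All values of D and its limits below are assumptions. Intervals use the normal multiplier 1.96.

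**Step 1. Error in one database's input.**
- Equation (5): SE(log D) = (ln D_upp − ln D_low)/(2 × 1.96). On the natural scale SE(D) ≈ D × SE(log D), or directly (D_upp − D_low)/(2 × 1.96).
- D = 20 years, limits 16 to 25: SE(log D) = ln(25/16)/3.92 = 0.114; SE(D) ≈ 20 × 0.114 = 2.28 years. The input is too small by a factor of 20.
- D = 0.5 years, limits 0.45 to 0.56: SE(log D) = ln(0.56/0.45)/3.92 = 0.056; SE(D) ≈ 0.5 × 0.056 = 0.028 years. The input is too large by a factor of 2. In months D = 6, and the same 0.056 is too small by a factor of 6.
- An interval symmetric on the natural scale behaves the same way. D = 5 years, limits 4 to 6: SE(D) = 2/3.92 = 0.510; SE(log D) = ln(6/4)/3.92 = 0.103; ratio 4.9, about D.

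**Step 2. Pooled result, databases that agree.** D = 4.8, 5.0, 5.3 years; limits 4.0–5.8, 4.3–5.8, 4.2–6.7. The square roots of equation (5) are 0.095, 0.076, 0.119; the natural-scale standard errors are 0.459, 0.383, 0.638 years. Random effects, REML:

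| Analysis | Pooled D (95% CI), years | I² | Weights, % |
|---|---|---|---|
| log D, square root of (5) | 4.99 (4.50–5.54) | 0% | 32/49/20 |
| D, natural-scale SE, any unit | 4.98 (4.46–5.51) | 0% | 34/49/18 |
| D, item 3 as written, in years | 5.03 (4.75–5.30) | 81% | 34/36/31 |
| D, item 3 as written, in months | 5.03 (4.75–5.32) | 99.9% | 33/33/33 |

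As written, the interval in years has width 0.55 against 1.05, about half, and agreement is reported as marked heterogeneity.

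**Step 3. Pooled result, databases that differ.** D = 4.0, 5.0, 6.5 years; limits 3.4–4.7, 4.4–5.7, 5.0–8.4. The consistent natural-scale analysis gives 4.98 years (3.72–6.24), Q 9.5, I² 79%, weights 38/38/24%, in every unit. Item 3 as written gives 5.16 years (3.74–6.58), Q 266, I² 99.2%, near-equal weights in years; in months Q is 38,370 and I² about 100%. The interval is slightly wider here, not narrower.

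With short survival (D = 0.40, 0.50, 0.60 years; limits 0.36–0.44, 0.42–0.60, 0.55–0.655), the consistent analysis gives I² 94.4% in any unit. As written it is 77.0% in years and 99.8% in months.

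**Step 4. Typical size with no true heterogeneity.** Simulating three databases with SE(log D) = 0.114 and DerSimonian–Laird pooling, the median ratio of the as-written to the correct pooled SE was about 0.84 at both D = 5 and D = 20 years. Coverage was about 82% against 96%, and I² was typically above 90%. At D = 0.5 years the ratio was about 2.

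The results at 5 and 20 years can be checked by hand. When the stated within-database variance is far too small, tau² is close to the sample variance of the three estimates, so the pooled SE is about s/√3 on 2 degrees of freedom. Its median relative to the true SE is √(ln 2) = 0.83, and the coverage of ±1.96 SE is 1.96/√(2 + 1.96²) = 0.81. Neither depends on D, which is why 5 and 20 years agree.

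**The case against.** The fault is conditional and partly inferred. Item 3 names only one scale, log D, and on that scale equation (5) is the right source. Equation (5) is also plainly labelled as a log-scale quantity, so whoever writes the code may notice the mismatch and use a natural-scale error instead. That may happen, but the text does not say so: it names one source of standard errors for a step whose scale it leaves open.

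A reader might infer from step 1 that the pooled interval would be twenty or five times too narrow. The documents do not support that. Those factors describe one database's input, and each database keeps its own Brookmeyer–Crowley interval. The planned model is random effects, where tau² restores most of the width. The full factor would survive only where tau² is estimated as zero, which in practice limits it to short durations analysed in years.

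A reader might also infer that the study's main comparison is invalid. It is not: the indirect prevalence in each database and its meta-analysis in item 4 do not use pooled D. For the closing product of pooled incidence and pooled duration no interval is specified, so only its value can be affected, and in the examples pooled D moves little.

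Items 3 and 4 speak of standard errors while equations (5) and (3) give variances. This is wording: the square root is clearly intended. Choosing the scale by skewness is a common diagnostic in a study that tests no hypothesis; the difficulty is that one of the two outcomes has no valid input.

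**Conclusion.** The point holds for the natural-scale branch of item 3. If D is pooled untransformed with equation (5) as written, the weights, interval, Q and I² are wrong and can depend on the time unit. The main damage is to the heterogeneity measures and the interval: typically a pooled SE of about 0.84 of the correct one and coverage of about 82% instead of 96% for durations of 5 to 20 years, and an interval about twice too wide at 0.5 years analysed in years. The pooled estimate itself shifts little (4.98 to 5.03 and 4.98 to 5.16 years in the examples).

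These sizes rest on assumed medians and limits, three contributing databases and a normal-based interval. The existence of the scale mismatch does not. The reach is limited to the pooled D, its heterogeneity measures and the closing indirect prevalence.

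**What to change.** In section 8.9, replace the conditional sentence and the input sentence of item 3 with: *Meta-analysis will be performed on log D, with TE = log D and seTE = the square root of equation (5), and the result back-transformed.* For clarity, state in item 4 that seTE is the square root of equation (3).

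This costs two sentences and no new data. It brings item 3 into line with item 4 and with the log-scale derivation in section 8.8.6, and it removes the need for a skewness criterion. Keeping a natural-scale option would also be consistent, but only with a stated standard error, (D_upp − D_low)/(2 × 1.96), and a rule for choosing the scale fixed in advance.

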Time from first diagnosis to death.

Data sources

- 1. Integrated Primary Care Information Project (IPCI), The Netherlands
- 2. Sistema d'Informació per al Desenvolupament de la Investigació en Atenció Primària (SIDIAP), Spain
- 3. Clinical Practice Research Datalink GOLD (CPRD GOLD), United Kingdom

Sample size

No sample size has been calculated. All patients with the disease will be included.

Data analyses

Population-level disease epidemiology: for each disease of interest, the complete point prevalence at the middle of the study period, i.e. 01/01/2016, will be calculated as well as incidence rate over the total study period.

For each patient only the first diagnosis of a disease will be considered. The date of this diagnosis can be before the observation period of the patient, i.e. before the period during which the patient is monitored in the database. A GP can have entered historical events, for example the diagnosis of an inherited disease. Also, information received from a patient's former GP might be imported. For this study, it is important to have as much patient's history as possible. The disease is considered to stay present during patient's observation period (and beyond). For point prevalence, all persons with a diagnosis before 01/01/2016 and in observation in the database at this date contribute to the numerator. The denominator is the total number of persons in observation on 01/01/2016. For the calculation of the incidence rate, only newly diagnosed patients (diagnosed within the observation time and within the study period) contribute to the numerator. The denominator is the total number of person-years at risk, i.e. the sum across all subjects included in the cohort of the observation time within the study period or until a diagnosis occurs.

Survival estimation: Kaplan Meier estimates for survival probabilities for time since first diagnosis. Median survival, as a proxy for disease duration, is the time point where the survival probability decreases to below 50%.

For all analyses a minimum cell count of 5 will be used when reporting results, with any smaller counts reported as "<5". Counts of zero will be reported.

From the incidence rate and median disease duration, the indirect prevalence will be calculated.

Results from the databases will be combined using random effects meta-analysis.

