8.8.1. Outcome cohorts

The outcome cohorts for the diseases will include only the first diagnosis date of each patient. This diagnosis date is cohort start date. Cohort end date is the end of the observation period of the patient.

Based on birth date of the patient and date of first diagnosis, age at diagnosis will be determined. Age will be categorized into 0 - 17 year (paediatric) and 18 year and older (adult). For each disease, if feasible, three outcome cohorts will be generated:

- patients with first diagnosis at any age •
- patients with first diagnosis at paediatric age
- patients with first diagnosis at adult age

All analyses described below will be done for each of these cohorts, under restriction of the minimum cell count criterion, i.e. for outcome cohorts with less than 5 subjects no analyses will be done.

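### The minimum cell count of 5, set for reporting, also decides which databases enter the pooled prevalence and incidence; in sparse strata this generally biases the pooled rate upward, and zero counts are handled inconsistently

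*Protocol*

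**What the plan says.** The protocol's abstract (section 3) presents the threshold as a disclosure rule: "For all analyses a minimum cell count of 5 will be used when reporting results". Smaller counts are masked, but zero is exempt: "Counts of zero will be reported".

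Section 8.8.1 turns the threshold into a condition for analysis: "for outcome cohorts with less than 5 subjects no analyses will be done". Zero is not exempted there. The same section asks for three cohorts per disease (any age, paediatric, adult), so sparse cells are foreseen.

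Section 8.9 carries the rule into the synthesis. A database may drop out of any of the four pooled quantities, and one of the two reasons offered is a small count: "because the number in a numerator might be below the minimum value of 5". The consequence is stated plainly: "Meta-analysis will be done with estimates available". Items 1 and 2 of that list are pooled direct prevalence, "using as input the numerators and denominators utilised to calculate the point prevalence in each database", and pooled incidence, with "input the total number of events and the total number of person years in each database".

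Section 11 (limitations) does not mention this selection.

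**The concern.** A disclosure rule hides a number from the reader. It need not remove the database from the model. In 8.9 it does, and whether a database stays depends on its own numerator, which is the quantity being pooled. Low counts leave and high counts remain, so the missing estimates are informative. Where true rates differ between countries, the country at the low end is the likeliest to be left out, and the heterogeneity measures are then computed without it.

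The abstract allows zeros to be shown, whereas 8.8.1 and 8.9, read literally, drop them. Yet no cases among more than a million people is information about the rate, and a count of zero with its denominator is a usable input for both pooled quantities.

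At stake are the pooled direct prevalence and pooled incidence for the rarest disease and age cells, which serve objectives 1 and 2 of the study.

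**Working it through.** The protocol gives no expected counts, disease rates or sample size, so there is no stated figure to reproduce.

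**Inputs.** Active subjects from Table 3: CPRD GOLD 3.0 million, IPCI 1.3 million, SIDIAP 5.8 million (total 10.1 million). They stand in for persons under observation on 01/01/2016. Study period: 13 years. All disease rates below are assumptions.

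**Rate at which the rule bites.** A count of 5 corresponds to 5/N:
- IPCI: 5/1.3 million = 0.38 per 100,000
- CPRD GOLD: 5/3.0 million = 0.17 per 100,000
- SIDIAP: 5/5.8 million = 0.09 per 100,000

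For incidence, dividing by 13 years gives about 0.030, 0.013 and 0.007 per 100,000 person-years.

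**One database.** For a Poisson count X with mean m, the selection ratio is E[X | X ≥ 5]/m. It is 1.91 at m = 3, 1.31 at m = 5, 1.06 at m = 8 and 1.02 at m = 10.

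**Three databases, one common rate.** Counts are Poisson with means proportional to 3.0, 1.3 and 5.8. The pooled rate is total cases over total persons among the databases kept, divided by the true rate and averaged over the simulated sets that leave something to pool.

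| Expected cases: IPCI / CPRD GOLD / SIDIAP | All counts below 5 dropped | Only 1–4 dropped, zeros kept |
|---|---|---|
| 1 / 2.3 / 4.5 | 1.54 | 0.97 |
| 2 / 4.6 / 8.9 | 1.12 | 1.09 |
| 3 / 6.9 / 13.4 | 1.06 | 1.05 |
| 4 / 9.2 / 17.8 | 1.04 | 1.03 |
| 5 / 11.5 / 22.3 | 1.025 | 1.02 |

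At 8 expected cases in IPCI the excess is 0.7%. In the first row, with all counts below 5 dropped, 49% of simulated sets leave no database to pool. With every count kept, the ratio is 1.00 throughout.

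**Unequal rates.** Assume 2.0 (CPRD GOLD), 1.5 (SIDIAP) and 0.1 to 0.3 (IPCI) per 100,000. Expected counts are 60, 87 and 1.3 to 3.9. The chance that IPCI falls below 5 is 99% at 0.1 and 65% at 0.3.
- Crude pooling without IPCI: 147/8.8 million = 1.67 per 100,000. With IPCI: 148.3/10.1 million = 1.47, up to 150.9/10.1 million = 1.49. Ratio 1.14 to 1.12.
- DerSimonian-Laird on log rates: 1.72 without IPCI. With IPCI: 1.36, 1.27 and 1.28 at IPCI rates of 0.1, 0.2 and 0.3. Ratio 1.26 to 1.35.
- REML on the same inputs: ratio 1.61 to 2.11. Section 8.9 names the functions but not the variance estimator, so the size under the planned model is not fixed by the protocol.

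**The case against.** The strongest reply is that nothing in the protocol shows the problem will occur. Table 3 justifies all three databases by sufficient feasibility counts, the bias is negligible above about 10 to 15 expected cases, and a 6% excess at 3 expected cases is small beside the Poisson error of such counts. This stands as a limit on scope. It does not remove the point: the feasibility column shows no counts, and 8.8.1 and 8.9 themselves anticipate counts below 5.

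It can also be said that the main objective is the comparison of direct and indirect estimates, that analyses are done in each database first, and that the rule is declared in advance. This is fair, but pooled prevalence and incidence are reported in their own right. The threshold also acts separately on the prevalence and incidence numerators, so the pooled direct and indirect values may rest on different databases.

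Sites return only aggregated results, so true small counts may never reach the pooling team. That is a reason to use bounds for 1 to 4; it is no reason to discard a zero that may be disclosed.

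Three stronger readings are tempting and not supported:
- A reader might infer that zero-count databases are definitely dropped. The abstract says zeros are reported, so the documents conflict and do not settle it.
- A reader might infer that the bias is always upward. If zeros stay and only 1 to 4 are dropped, the ratio at 1 expected case is 0.97.
- A reader might infer that a low-rate country vanishes from the study. It is missing only from the pooled figure; results are still given by database, with small counts shown as masked.

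**Conclusion.** The point holds for sparse strata. A reporting threshold has become outcome-dependent selection into the pooled prevalence and incidence, with no handling planned. Under a common rate and Table 3 sizes the excess is about 12%, 6% and 2.5% at 2, 3 and 5 expected cases in the smallest database, and below 1% at about 8. At about 1 expected case the direction depends on the treatment of zeros.

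With unequal rates it is larger: about 1.1 to 1.35 times with crude or DerSimonian-Laird pooling under the assumed rates. A reader might compute 1.8 to 2.6 times from the unweighted geometric means of those rates: √(2.0 × 1.5) = 1.73 against (2.0 × 1.5 × 0.1)^(1/3) = 0.67 and (2.0 × 1.5 × 0.3)^(1/3) = 0.97. The planned random-effects model does not give every database equal weight regardless of its case count, and the assumed 5- to 20-fold difference between countries has no basis in the protocol, so that range should not be used as the size of the problem.

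Which cells are affected cannot be told from the protocol. The conflict on zero between the abstract and sections 8.8.1 and 8.9 needs resolving whatever the counts turn out to be.

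**What to change.** In 8.8.1 and 8.9, for items 1 and 2, limit the <5 rule to reporting and align both sections with the abstract:
- A database with 0 cases enters metaprop and metarate with 0 and its denominator, under a model that accepts zeros (for example a binomial or Poisson GLMM). Name that model and its estimator in 8.9.
- For masked counts of 1 to 4, fit the pooled model with all masked counts set to 1 and again with all set to 4, and report the range. With inverse-variance weights the pooled value need not move steadily with the masked count (the DerSimonian-Laird values above fall from 1.36 to 1.27 and then rise to 1.28), so present it as a sensitivity range.
- Label any pooled value that omits a database as restricted to databases with at least 5 cases.

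Median survival needs observed cases, so leaving very small cohorts out of items 3 and 4 can stay.

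The cost is a few sentences and two extra model runs for the affected cells. No masked count is disclosed. The downside is a range instead of a single pooled value in the sparsest strata.

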8.2 Study Setting and Data Sources

For this study, suitable data sources should include individuals who can be considered as a representative sample of the general population and have the potential for long observation periods for subjects. Therefore, we focus on primary care data sources and hospital data sources are not included. Lifelong observation of patients is not available in any of the data sources within the DARWIN EU network, however, patients in primary care databases will often have several years of observation time. Also history of diagnoses before subject's observation time might be recorded. In addition, data sources should have a good recording of mortality.

When it comes to assessing the reliability of data sources, the data partners were asked to describe their internal data quality process on the source data as part of the onboarding procedure. In addition, they are asked to share the results from three data quality assurance package: CdmOnboarding, Data Quality Dashboard (DQD) and DashboardExport. The latter exports a subset of analyses from the Achilles tool (https://github.com/OHDSI/Achilles), which systematically characterizes the data and presents it in a dashboard format to ease the detection of potential quality issues. The generated data characteristics such as age distribution, condition prevalence per year, data density, measurement value distribution can be compared against the national healthcare data. CdmOnboarding creates a report with select characterisation of the clinical data within the database and details on mapping coverage statistics that are closely inspected upon onboarding. DQD provides more objective checks on conformance and plausibility, applied consistently across the data sources.

For eligible data sources within the DARWIN EU network, counts of initially suggested diseases were produced. This resulted in selecting the three primary care databases presented in Table 3.

	D2.2.3 - Study Protocol for P2-C1-013	
EUM	Author(s): [name], [name]	Version: 2.0
		Dissemination level: Public

Table 3. Description of the selected Data Sources.

Country	Name of Database	Justification for Inclusion	Health Care setting	Type of Data	Number of active subjects	Feasibility count of disease (if relevant)	Data lock for the last update

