United Kingdom	CPRD GOLD	Sufficient feasibility counts, sufficiently long median duration of observation periods, good recording of mortality	Primary care	EHR	3.0 million		Source data 01/07/2023
the Netherlands	IPCI	Sufficient feasibility counts, sufficiently long median duration of observation periods, good recording of mortality	Primary care	EHR	1.3 million		Source data 23/09/2023
Spain	SIDIAP	Sufficient feasibility counts, sufficiently long median duration of observation periods, good recording of mortality	Primary care	EHR	5.8 million		Source data 30/06/2023

Study Period

Study period is from January 1st, 2010, to December 31st, 2022.

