8.3 Follow-up

For all individuals in the databases, the observation period is recorded, i.e. the period during which the individual is monitored. In the primary care databases used in this study, it is the period the individual is registered in the GP practice.

• For the incidence estimation, the follow-up is the part of patient's observation period that overlaps with the study period. Only first diagnoses which fall within this follow-up period will contribute to

the incidence numerator. The follow-up period will contribute time at risk to the person-years denominator, restricted to the time before the first diagnosis of the relevant disease, if present.

- For the direct estimation of the point prevalence, a disease diagnosed before an individual's observation period, if present, will also be captured. Diagnoses before the observation period can be present if a GP has received information about the patient's history from the former GP, or if a GP enters historical information, e.g. the diagnosis date of an inherited disease. However, individuals can only contribute to the point prevalence numerator and denominator if the time point used to assess the point prevalence is within their observation period.
- In the survival analysis, the follow-up of patients starts at the first diagnosis of the disease of interest and ends at patient's death, end of patient's observation period or end of the study period, whatever comes first.

Further information on follow-up time is given in Table 4.

	D2.2.3 - Study Protocol for P2-C1-013			
EUM	Author(s): [name], [name]	Version: 2.0		
		Dissemination level: Public		

Table 4. Operational Definition of Time 0 (index date) and other primary time anchors.

Study population name(s)	Time Anchor Description	Number of entries	Type of entry	Washout window	Care Setting ¹	Code Type ²	Incident with respect to
Total population	Start of FU: latest of: - entry in database - start of study period (01/01/2010) End of FU: earliest of: - date of mortality - end of patient's observation period, i.e. deregistration of patient or end of GP data contribution - end of study period (31/12/2022)	1	NA	NA	PC, IP and OP	NA	NA

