8.4 Study Population with inclusion and exclusion criteria

For the incidence and prevalence estimations, the complete database population will be included.

For disease duration, all patients with the diagnosis of interest will be included, without any exclusion criteria.

Inclusion criteria are described in Table 5.

Criterion	Details	Assessment window	Care Settings ¹	Code Type	Applied to study populations:
Patients with a disease diagnosis	Earliest recording of disease diagnosis will be identified, this can be before or during observation time	Complete history and observation period of patient	PC, IP and OP	SNOMED code	Patients with disease diagnosis
Pediatric patients	Earliest recording of disease is at age 0-17	Complete history and observation period of patient	PC, IP and OP	SNOMED code	Patients with disease diagnosis at paediatric age
Adult patients	Earliest recording of disease is at age 18+	Complete history and observation period of patient	PC, IP and OP	SNOMED code	Patients with disease diagnosis at adult age

¹IP = inpatient, OP = outpatient, NA = not applicable, PC = primary care

No exclusion criteria are applied

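### The indirect estimate needs an observed Kaplan-Meier median and a finite upper limit; for long-lasting diseases censoring may prevent either, and the protocol's only response is to pool what is left

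*Protocol*

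**What the plan says.** The objective (section 7) is to compare direct and indirect prevalence for five diseases. The indirect estimate is P = I x D, with D the Kaplan-Meier median carrying a Brookmeyer-Crowley 95% interval (8.8.5, 8.8.6). Equation (5) obtains Var(log D) from the logs of the lower and upper limits of that interval. Equation (3) passes it to Var(log P), and section 8.9 passes both to metagen.

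On the length of follow-up, section 8.2 says "Lifelong observation of patients is not available in any of the data sources within the DARWIN EU network", and "Study period is from January 1st, 2010, to December 31st, 2022". The survival clock itself has no lower calendar limit: "Time zero for the survival analysis is the date of first diagnosis" (8.8.5), "Earliest recording of disease diagnosis will be identified, this can be before or during observation time" (Table 5), and "For disease duration, all patients with the diagnosis of interest will be included, without any exclusion criteria" (8.4). The study period caps only the end of survival follow-up.

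Section 8.9 notes that a database may give no estimate, for instance because "the median disease duration might not be observed in the available data". Its response is to run the meta-analysis on the estimates that exist. It names no other duration measure and does not mention a median that is reached while its upper limit is not. As a last step it multiplies the combined incidence by the combined median.

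**The concern.** The estimator is least available where duration is longest, which is the setting a study of chronic disease most needs to cover. Two failures are possible:

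- The median is not reached. There is then no indirect prevalence for that disease, age group and database.
- The median is reached but its upper limit is not. A point estimate of P exists, but equation (5) gives no variance, so there is no interval for P and no usable weight for D or P in metagen.

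The omission is also not neutral. A database tends to drop out because survival is long or deaths are few. The pooled median then leans towards shorter survival, and pooled direct prevalence may use three databases while pooled indirect prevalence uses fewer. The closing product in 8.9 can multiply an incidence from one set of databases by a median from another.

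**Working it through.** The protocol states no median, death rate, disease count or precision target, so there is no figure of its own to reproduce.

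**1. Equation (5).** Illustrative limits of 8 and 20 years give ((ln 20 - ln 8)/3.92)^2 = (0.916/3.92)^2 = 0.055. With limits of 8 years and not reached, the expression is infinite, and so are Var(log P) and the standard error meant for metagen.

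**2. Patients diagnosed within the study period.** 01/01/2010 to 31/12/2022 is 13 years. Under a constant hazard, S(13) = 0.5 needs ln 2/13 = 0.053 per year. For true medians of 5, 10, 20, 40 and 60 years, S(13) = exp(-13 ln 2/median) = 0.16, 0.41, 0.64, 0.80 and 0.86.

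**3. Simulation, incident patients only.** Assumptions not in the protocol: even accrual over 13 years, exponential survival, 5% deregistration per year. 1,000 runs, log-type limits:

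| True median | n | Median reached | Upper limit finite |
|---|---|---|---|
| 6 y | 100 | 99% | 42% |
| 8 y | 100 | 90% | 6% |
| 10 y | 100 | 70% | 0.4% |
| 15 y | 100 | 26% | 0% |
| 10 y | 300 | 88% | 6% |

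With untransformed limits at n = 100, the upper limit is finite in about 75% of runs at 6 years, 30% at 8 years, 9% at 10 years and essentially 0% at 15 years.

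**4. Simulation under the protocol's inclusion rule.** Time runs from first diagnosis, historical diagnoses are included and there is no delayed entry. Assumptions: exponential survival, diagnoses up to 60 years back and all recorded, registration starting evenly from 10 years before the study period to its end, mean registration 10 years, untransformed limits, 60 runs. Entries are proportions of runs with median reached / upper limit finite:

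| True median | n = 100 | n = 500 | Mean of medians reached, n = 500 |
|---|---|---|---|
| 5 y | 1.00 / 1.00 | 1.00 / 1.00 | 11.5 y |
| 10 y | 0.95 / 0.57 | 1.00 / 0.93 | 37 y |
| 20 y | 0.50 / 0.13 | 0.63 / 0.07 | 65 y |
| 40 y | 0.12 / 0.03 | 0.02 / 0.02 | too few runs |

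Sixty runs give a standard error of about sqrt(0.63 x 0.37/60) = 0.06 for the 0.63, so these are rough. At n = 500 and true medians of 5 years or more, the longest times were about 50 to 72 years, so the curve does run well past 13 years. The medians are too long because a patient must survive to be observed, yet is counted as at risk from diagnosis.

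**The case against.** The strongest reply is that survival follow-up is not confined to 13 years. It starts at first diagnosis, which may precede both 2010 and registration, and every diagnosed patient enters. This stands. A reader might infer from the study period that any disease with a median beyond 13 years cannot give one; the protocol's inclusion rule does not support that. In step 4 a 10-year median is nearly always reached, and its upper limit usually is at n = 500. The gain is smaller than it looks, because step 4 assumes complete recording of historical diagnoses, whereas section 11 says that not all GPs record them.

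The step 3 rates also depend on choices the protocol does not make. Section 8.8.5 names Brookmeyer-Crowley without a transformation, and n = 100 is an assumption. At n = 300 and a true median of 6 years, the upper limit is finite in 99% of runs even with log-type limits. Against this, section 8.8.1 allows analysis of any cohort of at least 5 patients, so small cohorts are within the plan.

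It can also be said that 8.9 already covers missing estimates, that the product of combined incidence and combined median survives one database's missing median, and that handling an open limit belongs in an analysis plan. The first two are true but leave the mismatch between database sets. The third carries less weight here, because the protocol itself fixes the estimator, the variance formula and the omission rule, and the variance formula fails in a foreseeable case.

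Finally, the study tests no hypothesis, so an indirect method that cannot be computed is itself reportable. That is fair, but it leaves the stated comparison unanswered for the disease concerned.

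**Conclusion.** The point holds as a gap in the plan. The indirect estimate requires an observed median, its interval and pooling also require a finite upper limit, and no fallback is given for either failure. The consequences are a lost comparison, a point estimate without an interval, or pooled direct and indirect prevalence from different databases.

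The size is conditional. For 100 incident patients with a true median of 10 years, the median is reached in about 70% of runs and the upper limit in about 0 to 10%, under exponential survival and 5% deregistration per year. Adding fully recorded historical diagnoses raises these rates, but without delayed entry the medians reached are then too long. In that setting failure is close to certain only for a much longer true median, such as 40 years.

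A reader might also infer that the inherited diseases on the list will give no result. The protocol has no survival, mortality or case-count figures, so which of the five diseases fail cannot be shown from it.

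**What to change.** 1. Keep the complete-prevalence comparison wherever D and both its limits are estimable. It is the stated target and should remain so.
2. When the median is reached but its upper limit is not, report the indirect point estimate without an interval and leave it out of metagen. When the median is not reached, say so for that disease, age group and database.
3. Compare pooled direct and pooled indirect prevalence over the same set of databases, and apply the same restriction to the product of combined incidence and combined median.
4. Add a supplementary horizon-limited comparison for every disease and database:
   - Direct: persons in observation on 01/01/2016 whose first diagnosis fell in the previous tau years, over all in observation that day.
   - Indirect: I x RMST(tau), where RMST(tau) is the area to tau under a Kaplan-Meier curve with delayed entry at the start of observation.
   - Horizon: tau = 5. A tau of 10 is possible, with the caveat that it reaches back to 2006, before the incidence period.
   - Variance: Var(log P) = 1/C + (SE(RMST)/RMST)^2, with C the incident cases and the Greenwood-based SE.

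In steady state, a population of N has (1 - P)N people at risk. They yield (1 - P)N x I cases per year, of whom a fraction S(u) are alive u years later. Summing over u from 0 to tau gives P_tau = (1 - P) x I x RMST(tau). The factor (1 - P) is negligible for rare diseases, and the curve is needed only up to tau.

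The cost is one extra numerator, a restricted mean and delayed-entry coding, all from data already held. The added comparison concerns recent-onset, not complete, prevalence and must be labelled so. It does not recover a lost complete-prevalence comparison, and its numerator still depends on how fully diagnoses before registration are recorded.
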